7. PARTICIPANT ENTRY

PRE-RANDOMISATION EVALUATIONS

Women will be evaluated by the mid-wife at the first visit in the antenatal clinic. An OGTT will be booked to test for early GDM in women with previous GDM considered at high risk of recurrence. Personal and medical history will be recorded. When women attend for the OGTT, blood and urine samples will be collected at 0 and 120 minutes.

INCLUSION CRITERIA

- Women with a history of GDM in previous pregnancies
- Age \geq 18 years
- Singleton pregnancy
- \leq 16 weeks gestation

EXCLUSION CRITERIA

- Women unable or unwilling to give consent
- Pre-gestational diabetes or use of anti-diabetic medication in the first visit
- Significant chronic medical conditions (cardiovascular, liver or kidney disease)
- Women participating in other medical trial
- Women who have undergone bariatric surgery
- Women with milk allergy/intolerance
- Women unable to speak/understand English

WITHDRAWAL CRITERIA

Participants will be free to withdraw at any time and are not required to give a reason.

8. ADVERSE EVENTS

Adverse Event (AE): Any untoward medical occurrence in a patient or clinical study subject.

Serious Adverse Event (SAE): Any untoward and unexpected medical occurrence that: results in death, is life-threatening, requires hospitalisation, results in persistent or significant disability or incapacity or a congenital abnormality or birth defect

Medical judgement should be exercised in deciding whether an AE is serious in other situations. Important AEs that are not immediately life threatening or do not result in death or hospitalisation but may jeopardise the subject or may require intervention to prevent one of the other outcomes listed in the definition above, should also be considered serious.

REPORTING PROCEDURES

All adverse events should be reported. Depending on the nature of the event the reporting procedures below should be followed. Any questions concerning adverse event reporting should be directed to the Chief Investigator in the first instance.

Non serious AEs

All such events, whether expected or not, should be recorded.

Serious AEs

An SAE form should be completed and faxed to the Chief Investigator within 24 hours. However, relapse, death and hospitalisations for elective treatment of a pre-existing condition do not need reporting as SAEs. All SAEs should be reported to the sponsor.

All SAEs should be reported to the Bromley Research Ethics Committee where in the opinion of the Chief Investigator the event was:

‘Related’, i.e. resulted from the administration of any of the research procedures; and

‘Unexpected’, i.e. an event that is not listed in the protocol as an expected occurrence.

Reports of related and unexpected SAEs should be submitted within 15 days of the Chief Investigator becoming aware of the event, using the NRES SAE form for non-IMP studies.

Local investigators should report any SAEs as required by their Local Research Ethics Committee and/ or Research and Development Office.

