- Women willing to participate in the study will be additionally requested to provide a second urine sample after the 120 min during the OGTT. When bloods are taken will also request HbA1c as part of the study's investigations.
- An OGTT to test for early GDM will be performed as part of routine care. During the OGTT blood samples are taken at 0 and 120 minutes. Additionally to glucose, which is normally measure during the OGTT, for study purposes we will request serum C-peptide at these time points.

Baseline insulin sensitivity and insulin secretion will be estimated through validated indices using serum glucose, insulin (or C-peptide) and urinary C-peptide.

After the participants have agreed to take part in the study and consent has been signed, data regarding anthropometrics, demographics and medical history will be collected. This information will be obtained by reviewing the participant's medical notes.

Anthropometric measurements will be recorded at the first antenatal routine visit, including: pre-pregnancy weight, weight at first visit and height. BMI will be calculated with this data.

Demographics, personal and medical history will be extracted from medical records, including: maternal age, ethnicity, education, smoking during pregnancy, medical history (hypertension, PCOS, other relevant condition), obstetric history (parity, stillbirth, macrosomia, pre-eclampsia).

3rd visit (Randomisation)

[figure not shown]
After obtaining the results from the OGTT, women will be categorised by their glycaemic status and divided into two independent cohorts:

- Women diagnosed with gestational diabetes (according to NICE guidelines 2015 diagnostic criteria): **early GDM** cohort
- Women with normal glucose tolerance or impaired glucose tolerance but not fulfilling GDM criteria: **Glucose tolerant** cohort.

Women from each cohort will be randomised into two groups after the results of the OGTT are obtained:

- Intervention group: Guar gum fibre supplement
- Placebo group: Cellulose supplement

Women will take the fibre supplement 3 times a day (with each main meal) until the 28th week of pregnancy when they will be re-evaluated.

4th visit (28th weeks gestation)

Glycaemic status will be assessed at 28 weeks gestation in the two cohorts of women participating in the study:

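### Pregnancy loss is not a named SAE, and death is both an SAE criterion and exempt from SAE reporting, so whether a loss without admission reaches the sponsor rests on one researcher's judgement

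*Combined protocol and SAP*

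**What the plan says.** Section 8 defines an adverse event as "Any untoward medical occurrence in a patient or clinical study subject". An SAE is "Any untoward and unexpected medical occurrence that" meets one of five criteria: "results in death, is life-threatening, requires hospitalisation, results in persistent or significant disability or incapacity or a congenital abnormality or birth defect".

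A second paragraph widens this. It says "Medical judgement should be exercised in deciding whether an AE is serious in other situations", and adds that important events without death or hospitalisation count as serious if they "may jeopardise the subject or may require intervention to prevent one of the other outcomes listed in the definition above".

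On reporting, the section opens with "All adverse events should be reported", names no recipient, and refers to the procedures that follow. For non-serious events the procedure is "All such events, whether expected or not, should be recorded". For SAEs it is a form to the Chief Investigator within 24 hours and a report to the sponsor. The SAE paragraph then exempts relapse, death, and admissions for elective treatment of an existing condition from SAE reporting.

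Women enter at 16 weeks or earlier (Section 7, inclusion criteria) and take the supplement "until the 28th week of pregnancy when they will be re-evaluated" (Section 6, 3rd visit). Section 9 states that participants are blinded and researchers are not. Stillbirth appears only as an item of baseline obstetric history (Section 6, 2nd visit). Pregnancy loss is nowhere an on-study event or outcome.

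**The concern.** The trial enrols only pregnant women, yet the single SAE criterion that clearly concerns the fetus is congenital abnormality or birth defect. A miscarriage or intrauterine death that does not endanger the woman and needs no admission fits none of the criteria without interpretation. The one criterion that might be stretched to cover it, death, is cancelled by the exemption a few lines later.

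Two things are at stake. The first is safety reporting: in a pilot of 40 women a single loss matters to the sponsor's oversight, and similar losses could be classified differently. Because the person classifying may know the allocation, such differences could fall unevenly between arms. The second is the analysis: in the glucose tolerant cohort a loss before 28 weeks removes the OGTT on which the primary outcome depends, and Section 9 gives no rule for pregnancies that end early.

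**Working it through.** The main check is a reading of the text, following one event through Section 8: a pregnancy loss after randomisation, managed without admission and not threatening the woman's life.

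1. **Listed criteria.** Life-threatening, hospitalisation and disability do not apply by construction. Loss of a pregnancy is not in itself a congenital abnormality or birth defect. That leaves death.
2. **Death.** The text does not say whose death counts. Adverse events are defined in the patient or subject, which points to the woman but does not exclude a wider reading. Under that wider reading the event meets the definition, but the reporting paragraph then says death need not be reported as an SAE. Neither reading secures a report.
3. **Unexpectedness.** The definition also requires the event to be unexpected. The protocol gives no list of expected events against which to judge this.
4. **Judgement clause.** The sentence on medical judgement carries no condition and allows the event to be classed as serious. The sentence after it is tied to jeopardy to the subject or to preventing a listed outcome. Neither mentions pregnancy loss.
5. **If judged serious:** form to the Chief Investigator within 24 hours, and report to the sponsor.
6. **If not judged serious:** recorded, with no stated route to the sponsor.

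Steps 5 and 6 differ only in the judgement made at step 4.

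**Window.** Sections 5 and 6 give 12 weeks of supplement ending at 28 weeks, and 28 - 12 = 16, so the start is near 16 weeks. The losses in question are those between about 16 and 28 weeks.

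**How likely is a loss?** The plan gives no loss rate, so there is no figure of its own to reproduce. Inputs: n = 40 (Sections 5 and 9) and an assumed loss probability p of 1-2% per woman over supplementation.

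Chance of at least one loss = 1 - (1 - p)^n

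| Assumption | Calculation | Result |
|---|---|---|
| p = 1%, n = 40 | 1 - 0.99^40 | 0.33 |
| p = 2%, n = 40 | 1 - 0.98^40 | 0.55 |
| Half of losses without admission, p = 1% | 1 - 0.995^40 | 0.18 |
| Half of losses without admission, p = 2% | 1 - 0.99^40 | 0.33 |

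The first two rows are the chance of any loss, in either arm and with or without admission. The last two use a further assumption, that half of losses involve no admission, only to show how the figure moves. The documents give no such share.

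**The case against.** The strongest reply is that Section 8 already provides a way to classify such an event as serious. The judgement sentence is unconditional, and most investigators would probably treat a fetal death as serious. The section also says that all adverse events should be reported. This stands as far as it goes: a reader might infer that a loss without admission can never reach the sponsor, and the text does not support that. What the reply shows is that escalation is possible. It does not show that escalation is assured, because the general reporting sentence names no recipient and defers to procedures that, for non-serious events, require only recording.

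A reader might also infer that losses would vanish from the efficacy data as unexplained missing outcomes. The documents do not support that either. Women are telephoned weekly, continue routine antenatal follow-up, and have all adverse events recorded, so the reason for a missing result would normally be known. The OGTT point also applies only to the glucose tolerant cohort. The early GDM cohort has no second OGTT, and its insulin outcome comes from medical records.

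Finally, 33-55% is not the chance of an unreported loss. It covers losses with admission, losses that would be judged serious, and women on cellulose. With about 20 women on guar gum (assuming equal allocation), the chance of any loss among them is 18-33% (1 - 0.99^20 = 0.18; 1 - 0.98^20 = 0.33). This objection is correct, and the figure is used here only to show that a loss during the trial is plausible.

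**Conclusion.** The point holds in this form: pregnancy loss is not named as an SAE, and death is at once an SAE criterion and exempt from SAE reporting. Whether a miscarriage or intrauterine death without admission is escalated therefore depends on case-by-case judgement by unblinded researchers. This follows from the rules as written and needs no assumption about how often losses occur.

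The size is known only loosely. At an assumed 1-2% rate, the chance of any loss among 40 women is 33-55%. The number that would go unescalated cannot be estimated from the documents. The correction is worth making because the trial population is entirely pregnant and the change is small. The effect on the analysis is secondary and confined to the glucose tolerant cohort.

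**What to change.** 1. In Section 8, add miscarriage and intrauterine death or stillbirth to the SAE list, from randomisation to last study contact. Include neonatal death if it occurs before that contact.
2. Reconcile the sentence exempting death from SAE reporting with the SAE definition, so that it cannot remove these events. Without this step, the first change could be undone by the exemption.
3. Tabulate pregnancy losses by arm across both cohorts. In the glucose tolerant cohort, show women whose pregnancy ends before the 28-week OGTT separately from other missing outcomes.

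The cost is an edit to Section 8, a few more SAE forms and one table. No extra visit is needed, since the weekly calls and record review are already planned. Adding preterm delivery would go beyond the gap described here.

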1. STUDY SUMMARY

TITLE The use of soluble fibre for the prevention of gestational diabetes among high-risk women. A pilot study.

AIMS The primary aim of this study is to evaluate the effect of a soluble fibre supplement in the development of gestational diabetes in women at high-risk. The secondary aim will be to evaluate the effect of the soluble fibre supplement on glycaemic control in high-risk women who develop gestational diabetes in early pregnancy.

DESIGN We plan to conduct a randomised single-blinded controlled study to evaluate the effect of the consumption of soluble fibre, from early to mid-pregnancy, on the incidence of gestational diabetes, insulin sensitivity, insulin secretion and metabolic control in GDM diagnosed participants.

POPULATION We will be studying women with diagnosis of gestational diabetes in previous pregnancies, (considered as high-risk) aged >18 years.

ELIGIBILITY Women over 18 years old with a history of gestational diabetes in previous pregnancies will be eligible to apply to this study. After first assessment, eligible women will be split according to their glycaemic status in women with and without early gestational diabetes.

TREATMENT Participants in the treatment arms will be taking 5 gr of Guar gum fibre supplement with meals three times a day (total daily 15 g). Participants in the placebo arms will be taking 5 gr of Cellulose three times a day (total daily dose 15 g).

DURATION Participants will be involved for 12 weeks.

OUTCOME MEASURES

In women with normal glucose tolerance at first assessment:

Primary outcome: Gestational diabetes (yes/no) at 28 weeks gestation.

Secondary outcomes: Insulin sensitivity and insulin secretion at 28 weeks gestation.

In women with early gestational diabetes (diagnosed at first assessment):

Primary outcome: Glycaemic control assessed the need of insulin treatment (yes/no)

Secondary outcomes: In women requiring insulin treatment: days-to-insulin and total daily insulin dose.

INTRODUCTION

GESTATIONAL DIABETES

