6. ASSESSMENT AND FOLLOW UP

Women will be assessed by the researchers at four different visits. At the first antenatal visit, the general care team will mention the study, if the patient consents, she will then be approached by the researchers to explain the study protocol. At the second visit, when the OGTT is performed, women who decided to take part in the study will sign the consent form. At the next antenatal visit where results from the OGTT are explained, women included will be randomised. The last research visit will take place at 28 weeks gestation. Additionally, they will be contacted weekly, by telephone to assess compliance and confirm willingness to participate in the study. All participating women will continue to attend routine follow up by the Obstetrics team at the antenatal clinic. Women diagnosed with GDM in early pregnancy will continue their routine care under the Obstetric team at Queen Charlotte's Hospital. We will be collecting information regarding treatment from the notes taken at this follow-up visits.

1st visit (≤16 weeks gestation)

Women with a previous history of GDM will be considered at high risk of recurrence and will be referred to the antenatal clinic before 16 weeks of pregnancy. At this first visit, the direct care team will inform them about the study and ask them if they are willing to speak with a member of the research team. If they agree, a research team member will explain the protocol and invite them to participate in the study. An information sheet will be provided and women will have time to consider if they are willing to participate and inform the research team at their next antenatal visit.

2nd visit

Women who decide to participate will inform the research team when they attend their second antenatal visit, when an OGTT is to be performed. In this visit, women willing to participate will be asked to sign a consent form.

As part of the standard pregnancy care, these women will be booked for GDM early screening. The following investigations will be performed as part of their usual NHS care:

- Blood tests: full blood count, renal function. GAD antibodies can be requested in women in whom type 1 diabetes is suspected.
- Urine sample to test for proteinuria, glycosuria, leucocytes and nitrates.

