- Women from the **Glucose tolerant cohort** will undergo a second OGTT. Blood and urine samples will be collected at 0 and 120 minutes. Glycaemic status will then be assessed with the endpoint being the diagnosis of GDM (yes/no). Insulin sensitivity and insulin secretion will be estimated using the same parameters as in the first visit. As part of the study, women will be weight to calculate BMI and gestational weight gain at 28 weeks gestation. The research team will have their last face to face visit with the participant to discontinue the intervention and answer any potential questions about the study.
- In women in the **Early GDM cohort**, glycaemic control will be assessed by the need of insulin treatment (yes/no) and in those requiring insulin the days-to-treatment (insulin) and total insulin dose will be recorded. Data will be obtained by reviewing medical records. As part of the study, women will be weight to calculate BMI and gestational weight gain at 28 weeks gestation. The research team will have their last face to face visit with the participant to discontinue the intervention and answer any potential questions about the study.

PROCEDURES

Women will be advised to fast for 10 hours the night before the oral glucose tolerance test. They will also be advised not to restrict carbohydrate ingestion the three days prior to the OGTT. At the antenatal clinic, blood samples will be collected at baseline (0 min) and at 120 min after the administration of an oral load of 75 g of glucose.

In the baseline sample other parameters will also be determined. Creatinine and HbA1c will measure in all participants and GAD antibodies will be requested in women in whom type 1 diabetes is suspected.

Serum insulin and C-peptide will be collected at 0 and 120 min during the OGTT.

Women will be advised to void their first urine before attending the antenatal clinic. Second-void fasting urine sample will be collected at 0 min during the OGTT. A second urine sample will be collected at 120 min. Urinary C-peptide will measure in these samples will be transfer to boric acid containers, the aliquoted into 1 ml cryotubes and stored at -80 °C until analysis. Serum creatinine will be collected at baseline (0 min) and measure in the central lab. The urinary C-peptide creatinine ratio (UCPCR) will be calculated using these data.

ASSESSMENTS

(i) Gestational diabetes

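### Birth defect is a listed serious adverse event, but the plan states no SAE reporting window and describes no collection of birth outcome after research contact ends at 28 weeks

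*Combined protocol and SAP*

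**What the plan says.** **What counts as serious.** Section 8 (Adverse Events) lists a "congenital abnormality or birth defect" among the criteria that make an event serious. It requires every adverse event to be reported. SAEs go to the Chief Investigator within 24 hours and also to the sponsor. Related and unexpected SAEs go to the ethics committee within 15 days of the Chief Investigator learning of them. The section states no start or end date for these duties. It defines an adverse event as occurring in a patient or study subject and does not say whether the fetus or newborn counts.

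**When research contact ends.** The Study Summary (Duration) says "Participants will be involved for 12 weeks". Section 6 (Assessment and Follow Up) has women take the supplement "until the 28th week of pregnancy when they will be re-evaluated". It then says, for both cohorts, "The research team will have their last face to face visit with the participant to discontinue the intervention". Between visits women are "contacted weekly, by telephone to assess compliance and confirm willingness to participate in the study"; asking about adverse events is not a stated purpose of these calls.

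**What is taken from routine records.** Routine obstetric care continues for all women. The information that Section 6 plans to draw from follow-up notes concerns treatment, and the outcome review of records in the early GDM cohort concerns insulin. The outcome lists in the Study Summary and Section 5, and the analyses in Section 9, contain metabolic and treatment measures only.

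**The concern.** The protocol names a class of serious event that may be recognised only at birth or later, in a trial of a supplement taken during pregnancy, yet it describes no step that would find such an event after 28 weeks. Two things are at stake.

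- **Interpretation.** A final safety section with no birth defects listed could mean that none occurred or that nobody looked. The plan gives no means of telling these apart, because the number of births examined would be unknown.
- **Even-handedness.** Section 9 says that participants, but not researchers, are blinded. If late events come in only when someone happens to hear of them, knowledge of the arm can influence which ones are noticed or passed on.

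The Introduction argues for the intervention partly from perinatal outcomes such as macrosomia, birth weight and caesarean section. A reader of the pilot may therefore expect it to say something about the births.

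**Working it through.** The documents state no safety rate or safety sample size, and Section 9 says that the 40 women were chosen without a power calculation. There is no planned figure to reproduce. The check is a timeline, followed by illustrative arithmetic on what a look-up could deliver.

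**Timeline**

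1. Latest gestation at entry is 16 weeks (Section 6, first visit; Section 7, inclusion criteria). Participation lasts 12 weeks (Study Summary). 16 + 12 = 28 weeks, which agrees with the last research visit.
2. Assume birth at 37 to 40 weeks (the documents give no figure). The gap after the last visit is 37 − 28 = 9 weeks to 40 − 28 = 12 weeks, plus the newborn period.
3. Routes by which an event in that gap could reach the trial:
   - Research visits: none after 28 weeks.
   - Weekly calls: for compliance and willingness to continue, with none described after the intervention stops.
   - Review of notes: treatment and insulin data only.
   - The general duty in Section 8: no end date, so a case that came to the team's notice could still be reported, but nobody is tasked with looking.

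Only the last route is open, and it is passive.

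**What follow-up to birth would give**

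Assumptions: an even split, so about 20 women on guar gum; a complete look-up; event rates p of 1% to 5%, since the documents give none.

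Chance of at least one event among n women = 1 − (1 − p)^n:

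| p | n = 20 | n = 40 |
|---|---|---|
| 1% | 18% | 33% |
| 2% | 33% | 55% |
| 3% | 46% | 70% |
| 5% | 64% | 87% |

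One-sided 95% upper limit with zero events = 1 − 0.05^(1/n):

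- n = 20: 1 − 0.05^(1/20) = 13.9%
- n = 40: 1 − 0.05^(1/40) = 7.2%

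Across these assumed rates, a recordable case among 40 women is plausible. The upper limits are far too wide to compare arms or to rule out a modest excess.

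**The case against.** The strongest reply is that Section 8 is a classification rule. It says how to grade an event once known and does not undertake to search for every category. Its duty to report has no cut-off, and the ethics clock starts when the Chief Investigator becomes aware of the event. Routine obstetric care continues after 28 weeks. No safety endpoint or birth-defect rate is planned, so no stated analysis fails.

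Much of this stands, and it rules out stronger readings that a reader might infer:

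- **That the trial cannot detect a birth defect, or would report none whatever happened.** An abnormality recognised before 28 weeks falls within the study period and is reportable. A later one could be reported if it came to the team's notice.
- **That all follow-up stops at 28 weeks.** Research contact stops; clinical follow-up does not.
- **That the protocol promises to ascertain birth defects.** It lists the category and makes no such promise.

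The available text is also incomplete. The timeline in Section 6 has a heading but no visible content, a figure at the third visit is not shown, and the consent pages were removed. What the consent form covers is unknown.

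The reply does not supply an active route to birth outcome. A duty without an end date still depends on someone hearing of the event, and continuing clinical care helps the trial only if its records are consulted for this purpose.

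**Conclusion.** The concern holds as a gap in ascertainment. Birth defect is a listed SAE category, the reporting window and the status of fetal and neonatal events are unstated, and the visible plan collects no birth outcome for any of the 40 women. Followed as written, the trial would learn of abnormalities first recognised at or after birth only by chance, so their absence from the report would carry no safety information.

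The 9-to-12-week gap rests on assumed birth at 37 to 40 weeks. The 13.9% and 7.2% limits are illustrations that assume an even split, complete look-up and no events. No efficacy result is affected. This is an inexpensive improvement that should be made; it does not invalidate the design.

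**What to change.** 1. Add to Section 6 one look-up of the delivery record for every randomised woman, recording live birth or stillbirth and any congenital abnormality. Gestation at delivery and birth weight are optional extras.
2. Report the results by arm as descriptive safety data only, with the number of records found as the denominator and no test between arms.
3. State in Section 8 that SAE reporting for pregnancy outcome runs to delivery and covers fetal and neonatal events. In the same edit, reconcile the definition, which makes death an SAE criterion, with the later sentence that exempts death from SAE reporting. As they stand, the handling of stillbirth or neonatal death is unclear.
4. Check that consent covers the look-up, and amend it if not.

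**Cost.** About 40 look-ups in hospital records of a kind the team already uses, with no extra visit or sample. The safety table closes roughly three months after the last 28-week visit (40 − 28 = 12 weeks, with term assumed at 40). The efficacy analysis need not wait. An abnormality recognised only after the delivery record is complete would still be missed, and the report should say so.

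### The SAE reporting rule exempts death without qualification, which contradicts the protocol's own SAE definition and the sentence that follows the exemption

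*Combined protocol and SAP*

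**What the plan says.** Everything relevant is in section 8, Adverse Events.

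- **Definition.** An SAE is "Any untoward and unexpected medical occurrence that: results in death, is life-threatening, requires hospitalisation", followed by disability and congenital abnormality. Death heads the list.
- **General rule.** "All adverse events should be reported. Depending on the nature of the event the reporting procedures below should be followed". Two procedures follow, one for non-serious and one for serious events. Non-serious events are only to be recorded.
- **Serious events, first route.** "An SAE form should be completed and faxed to the Chief Investigator within 24 hours".
- **Exemption.** The next sentence, which opens as an exception to that rule, says that "relapse, death and hospitalisations for elective treatment of a pre-existing condition do not need reporting as SAEs".
- **Serious events, second route.** Directly after the exemption: "All SAEs should be reported to the sponsor".
- **Third route.** "All SAEs should be reported to the Bromley Research Ethics Committee where in the opinion of the Chief Investigator the event was" both related and unexpected, with a time limit: "Reports of related and unexpected SAEs should be submitted within 15 days of the Chief Investigator becoming aware of the event".
- **Fourth route.** "Local investigators should report any SAEs as required by their Local Research Ethics Committee and/ or Research and Development Office".

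Questions about reporting go to the Chief Investigator. No other section limits or explains the exemption.

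**The concern.** The definition and the exemption cannot both be applied to the same event. A participant's death meets the first SAE criterion, yet the reporting rule says it need not be reported as one. The three sentences that set out the remaining routes come after the exemption and speak of all or any SAEs, so a reader cannot tell whether a death still goes to the sponsor, the ethics committee and the local offices, or to none of them.

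If site staff follow the exemption, the death loses at least the 24-hour form to the Chief Investigator. The general instruction to report all adverse events survives, but it points to the procedures below it, and the only procedure left is the non-serious one, which has no form, deadline or recipient. A death would then have a weaker stated route than an unplanned hospital admission. What is at stake is participant-safety oversight; no endpoint, sample size or efficacy analysis depends on it.

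**Working it through.** The plan gives no figure to reproduce and the point needs no event rate. The check is a comparison of the sentences in section 8, a search of the other sections for a limiting phrase, and a count of reporting routes.

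**Step 1: can the exemption be read so that it does not conflict?**

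- *By grammar.* The closing words about elective treatment make sense only with hospitalisations. Stretching the reference to a pre-existing condition over all three listed items is strained, and would still exempt some deaths that meet the definition.
- *As covering expected deaths only.* The definition already requires the event to be unexpected, so an expected death is not an SAE and needs no exemption. The exemption can have effect only on unexpected deaths. The available text also contains no list of expected events that names death.
- *As covering deaths counted as an endpoint.* Death is not an outcome in the study summary, in section 5 or in section 9.
- *As reflecting a population with high background mortality.* Section 7 excludes women with significant cardiovascular, liver or kidney disease.

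None of these removes the conflict. The word *relapse* in the same sentence has no defined meaning in this trial. That suggests, but does not prove, that the sentence came from another setting.

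**Step 2: how much reporting is displaced?** Section 8 states four SAE routes. The narrow reading takes the exemption to modify only the form rule just before it. The broad reading takes it to cover all reporting as an SAE.

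| Route | Death, narrow reading | Death, broad reading | Non-elective hospitalisation meeting the definition |
|---|---|---|---|
| 1. Form to Chief Investigator, 24 hours | displaced | displaced | kept |
| 2. Report to sponsor | kept | displaced | kept |
| 3. Ethics committee, 15 days, if related and unexpected | kept | displaced | kept |
| 4. Local ethics committee or R&D office, as locally required | kept | displaced | kept |
| **Displaced** | **1 of 4** | **4 of 4** | **0 of 4** |

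Routes 3 and 4 are conditional for any SAE, so the broad count is an upper bound.

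**Step 3: what is left for an exempted death?** The general duty to report adverse events and the referral of questions to the Chief Investigator. Neither supplies a form or a deadline for a death.

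**The case against.** The strongest reply is that the exemption names only an outcome. A fatal event will often have been life-threatening or have led to an unplanned admission first, and those criteria are not exempted. Such an event would still qualify as an SAE, which narrows the gap with a hospital admission. It does not close it: a death outside hospital may be recorded only as a death, and staff may reasonably apply the exemption to the fatal event as a whole.

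The upper end of the route count is also open to challenge. The local duty is set by outside bodies, so a sentence in the protocol cannot clearly remove it, and the sponsor sentence comes after the exemption and carries no exception. Both points have force. They make the broad reading less natural, but they do not rule it out, and the count measures ambiguity in the wording rather than harm.

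The wording is permissive: it does not forbid reporting a death as an SAE. Participants are telephoned weekly and remain under routine obstetric care, so a death would probably be noticed, and section 10 provides for sponsor audit. In a 12-week pilot of a fibre supplement in 40 women, a death is improbable. All of this is true and bears on how likely the defect is to matter. It does not settle what staff should do if a death occurs, because being noticed is not the same as having a stated form, deadline and recipient.

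It is also fair to say that this is better described as an internal contradiction than as a deliberate design decision, and that the section does not say whether fetal or neonatal death is covered. Removing one word from the exemption does not answer that second question.

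**Conclusion.** The concern holds. Section 8 defines a fatal event as an SAE, exempts death from SAE reporting without limit, and then requires every SAE to go to the sponsor. These sentences cannot all be followed. For a death, between 1 and 4 of the 4 stated routes are displaced, depending on a reading that the document does not settle; for a non-elective hospitalisation that meets the definition, none is.

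The conclusion rests on the text alone. The size rests on two assumptions: that the exemption is applied to the fatal event as a whole and, for the upper figure, that it reaches all SAE reporting and not just the form. It claims nothing about how likely a death is. The defect should be corrected despite its low probability, because reporting rules exist for rare and grave events and must be usable without interpretation.

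**What to change.** Delete death from the exemption sentence in section 8, under Serious AEs, so that a fatal event follows the same SAE reporting route as any other event that meets the definition. The definition, the 24-hour rule and the sponsor, ethics committee and local sentences then agree without further change.

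Relapse can be struck out in the same edit, since the trial gives it no meaning, although the reconciliation does not depend on it. The sponsor may also wish to state whether the rule covers fetal and neonatal death; that is a separate clarification.

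The cost is a one-sentence wording amendment and, at most, a rare extra SAE form. Outcomes, sample size and analyses are unchanged.
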